If a participant has confirmed radiographic progression (iCPD) as defined in Appendix 9, study intervention should be discontinued; however, if the participant is achieving a clinically meaningful benefit, an exception to continue study intervention may be considered following consultation with the Sponsor and after obtaining signed informed consent addendum. In this case, if study intervention is continued, tumor imaging should continue to be performed following the intervals as outlined in Section 1.3 and submitted to the iCRO.

[figure not shown]
A description of the adaptations and iRECIST process is provided in Appendix 9, with additional details in the iRECIST publication [Seymour, L., et al 2017]. A summary of imaging and treatment requirements after first radiologic evidence of progression is provided in [Table 6](#) and illustrated as a flowchart in [Figure 2](#).

Table 6 Imaging and Treatment after First Radiologic Evidence of Progressive Disease

	Clinically Stable		Clinically Unstable	
	Imaging	Treatment	Imaging	Treatment
First radiologic evidence of PD by RECIST 1.1.	Repeat imaging at 4 to 8 weeks to confirm PD.	May continue study intervention at the investigator's discretion and after the participant's consent.	Repeat imaging at 4 to 8 weeks to confirm PD per investigator's discretion only.	Discontinue treatment
Repeat tumor imaging confirms PD (iCPD) by iRECIST per investigator assessment.	No additional imaging required.	Discontinue treatment (exception is possible on consultation with Sponsor).	No additional imaging required.	Not applicable
Repeat tumor imaging shows iUPD by iRECIST per investigator assessment.	Repeat imaging at 4 to 8 weeks to confirm PD. May occur at next regularly scheduled imaging visit.	Continue study intervention at the investigator's discretion.	Repeat imaging at 4 to 8 weeks to confirm PD per investigator's discretion only.	Discontinue treatment
Repeat tumor imaging shows iSD, iPR, or iCR by iRECIST per investigator assessment.	Continue regularly scheduled imaging assessments.	Continue study intervention at the investigator's discretion.	Continue regularly scheduled imaging assessments.	May restart study intervention if condition has improved and/or clinically stable per investigator's discretion. Next tumor imaging should occur according to the regular imaging schedule.

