10.9 Appendix 9: Description of the iRECIST Process for Assessment of Disease Progression

Assessment at Screening and Prior to RECIST 1.1 Progression

Until radiographic disease progression based on RECIST 1.1, there is no distinct iRECIST assessment.

Assessment and Decision at RECIST 1.1 Progression

For participants who show evidence of radiological PD by RECIST 1.1 as determined by the investigator, the investigator will decide whether to continue a participant on study intervention until repeat imaging is obtained (using iRECIST for participant management (see [Table 6](#) and [Figure 2](#)). This decision by the investigator should be based on the participant's overall clinical condition.

Clinical stability is defined as the following:

- Absence of symptoms and signs indicating clinically significant progression of disease
- No decline in ECOG performance status
- No requirements for intensified management, including increased analgesia, radiation, or other palliative care

Any participant deemed clinically unstable should be discontinued from study intervention at site-assessed first radiologic evidence of PD, and is not required to have repeat tumor imaging for confirmation of PD by iRECIST.

If the investigator decides to continue treatment, the participant may continue to receive study intervention and the tumor assessment should be repeated 4 to 8 weeks later to confirm PD by iRECIST, per investigator assessment. Images should continue to be sent in to the central imaging vendor for potential retrospective BICR.

Tumor flare may manifest as any factor causing radiographic progression per RECIST 1.1, including:

- Increase in the sum of diameters of target lesion(s) identified at baseline to $\geq 20\%$ and ≥ 5 mm from nadir
Note: The iRECIST publication uses the terminology “sum of measurements,” but “sum of diameters” will be used in this protocol, consistent with the original RECIST 1.1 terminology.
- Unequivocal progression of nontarget lesion(s) identified at baseline
- Development of new lesion(s)

iRECIST defines new response categories, including iUPD (unconfirmed progressive disease) and iCPD (confirmed progressive disease). For purposes of iRECIST assessment, the first visit showing progression according to RECIST 1.1 will be assigned a visit (overall) response of iUPD, regardless of which factors caused the progression.

At this visit, target and nontarget lesions identified at baseline by RECIST 1.1 will be assessed as usual.

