New lesions will be classified as measurable or nonmeasurable, using the same size thresholds and rules as for baseline lesion assessment in RECIST 1.1. From measurable new lesions, up to 5 lesions total (up to 2 per organ), may be selected as New Lesions – Target. The sum of diameters of these lesions will be calculated, and kept distinct from the sum of diameters for target lesions at baseline. All other new lesions will be followed qualitatively as New Lesions – Non-target.

Assessment at the Confirmatory Imaging

On the confirmatory imaging, the participant will be classified as progression confirmed (with an overall response of iCPD), or as showing persistent unconfirmed progression (with an overall response of iUPD), or as showing disease stability or response (iSD/iPR/iCR).

Confirmation of Progression

Progression is considered confirmed, and the overall response will be iCPD, if ANY of the following occurs:

- Any of the factors that were the basis for the iUPD at the previous visit show worsening
 - For target lesions, worsening is a further increase in the sum of diameters of ≥ 5 mm, compared to any prior iUPD time point
 - For nontarget lesions, worsening is any significant growth in lesions overall, compared to a prior iUPD time point; this does not have to meet the “unequivocal” standard of RECIST 1.1
 - For new lesions, worsening is any of these:
 - An increase in the new lesion sum of diameters by ≥ 5 mm from a prior iUPD time point
 - Visible growth of new nontarget lesions
 - The appearance of additional new lesions
- Any new factor appears that would have triggered PD by RECIST 1.1

Persistent iUPD

Progression is considered not confirmed, and the overall response remains iUPD, if:

- None of the progression-confirming factors identified above occurs AND
- The target lesion sum of diameters (initial target lesions) remains above the initial PD threshold (by RECIST 1.1)

Additional imaging for confirmation should be scheduled 4 to 8 weeks from the imaging on which iUPD is seen. This may correspond to the next visit in the original visit schedule. The assessment of the subsequent confirmation imaging proceeds in an identical manner, with possible outcomes of iCPD, iUPD, and iSD/iPR/iCR.

Resolution of iUPD

Progression is considered not confirmed, and the overall response becomes iSD/iPR/iCR, if:

- None of the progression-confirming factors identified above occurs, AND

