- The target lesion sum of diameters (initial target lesions) is not above the initial PD threshold.

The response is classified as iSD or iPR (depending on the sum of diameters of the target lesions), or iCR if all lesions resolve.

In this case, the initial iUPD is considered to be pseudo-progression, and the level of suspicion for progression is “reset.” This means that the next visit that shows radiographic progression, whenever it occurs, is again classified as iUPD by iRECIST, and the confirmation process is repeated before a response of iCPD can be assigned.

Management Following the Confirmatory Imaging

If repeat imaging does not confirm PD per iRECIST, as assessed by the investigator, and the participant continues to be clinically stable, study treatment may continue and follow the regular imaging schedule. If PD is confirmed, participants will be discontinued from study treatment.

NOTE: If a participant has confirmed radiographic progression (iCPD) as defined above, but the participant is achieving a clinically meaningful benefit , an exception to continue study intervention may be considered following consultation with the Sponsor. In this case, if study intervention is continued, tumor imaging should continue to be performed following the intervals as outlined in Section 1.3 and submitted to the central imaging vendor.

Detection of Progression at Visits After Pseudo-progression Resolves

After resolution of pseudo-progression (ie, achievement of iSD/iPR/iCR), iUPD is indicated by any of the following events:

- Target lesions
 - Sum of diameters reaches the PD threshold ($\geq 20\%$ and ≥ 5 mm increase from nadir) either for the first time, or after resolution of previous pseudo-progression. The nadir is always the smallest sum of diameters seen during the entire study, either before or after an instance of pseudo-progression.
- Nontarget lesions
 - If nontarget lesions have never shown unequivocal progression, their doing so for the first time results in iUPD.
 - If nontarget lesions have shown previous unequivocal progression, and this progression has not resolved, iUPD results from any significant further growth of non-target lesions, taken as a whole.
- New lesions
 - New lesions appear for the first time
 - Additional new lesions appear
 - Previously identified new target lesions show an increase of ≥ 5 mm in the new lesion sum of diameters, from the nadir value of that sum

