 - Previously identified non-target lesions show any significant growth

If any of the events above occur, the overall response for that visit is iUPD, and the iUPD evaluation process (see Assessment at the Confirmatory Imaging above) is repeated. Progression must be confirmed before iCPD can occur.

The decision process is identical to the iUPD confirmation process for the initial PD, with one exception: If new lesions occurred at a prior instance of iUPD, and at the confirmatory imaging the burden of new lesions has increased from its smallest value (for new target lesions, the sum of diameters is ≥ 5 mm increased from its nadir), then iUPD cannot resolve to iSD or iPR. It will remain iUPD until either a decrease in the new lesion burden allows resolution to iSD or iPR, or until a confirmatory factor causes iCPD.

Additional details about iRECIST are provided in the iRECIST publication [Seymour, L., et al 2017].

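### At a first iUPD episode, Appendix 9 separates persistent from resolved progression by the target-lesion sum alone, so unchanged new or nontarget progression is classed as iSD or iPR

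*Combined protocol and SAP*

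**What the plan says.** Section 10.9 (Appendix 9) lists three ways to reach radiographic progression: growth of the target sum, "Unequivocal progression of nontarget lesion(s) identified at baseline", and new lesions. The first such visit "will be assigned a visit (overall) response of iUPD, regardless of which factors caused the progression".

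At the confirmatory scan, iCPD requires that a factor behind the iUPD has worsened or that a new progression factor has appeared. If neither has happened, two outcomes remain:

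- Persistent iUPD, if "The target lesion sum of diameters (initial target lesions) remains above the initial PD threshold (by RECIST 1.1").
- Resolution, if "The target lesion sum of diameters (initial target lesions) is not above the initial PD threshold". The visit is then iSD or iPR according to the target sum; only iCR needs every lesion to be gone. "In this case, the initial iUPD is considered to be pseudo-progression", and the level of suspicion starts afresh.

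For later iUPD episodes the process is the same with one declared exception. If new lesions occurred at an earlier iUPD and their burden has risen from its smallest value, resolution is blocked: "It will remain iUPD until either a decrease in the new lesion burden allows resolution to iSD or iPR".

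Section 3 limits iRECIST to Arm 1, for investigator treatment decisions and exploratory efficacy analyses. In Section 8.2.1.5, Table 6 has separate imaging and treatment rows for a repeat scan showing iUPD and for one showing iSD, iPR or iCR.

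**The concern.** The trigger has three possible causes, but the test of whether it persists looks at only one. If a new metastasis or nontarget growth was the sole cause, the target sum was below the threshold when iUPD was called. A finding that is still there and has not changed cannot then satisfy the persistence rule. It passes to resolution by default, although nothing has resolved.

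Two things follow. First, an unresolved lesion can coexist with an iSD or iPR visit, which can feed the exploratory iRECIST response and disease-control summaries. Second, the reset changes how the next scan is read: worsening that would have confirmed progression instead opens a new unconfirmed episode. The label also selects the row of Table 6 that applies.

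**Working it through.** There is no plan figure to reproduce. The check applies the Appendix 9 rules to each cause of iUPD, with every lesion unchanged at the confirmatory scan. The inputs are the trigger list, the two iCPD conditions, the persistence and resolution bullets, and the later-episode exception. For a nontarget-only or new-lesion-only cause, the target sum is by definition below the progression threshold.

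| Episode | Sole cause of iUPD | Result with all lesions unchanged |
|---|---|---|
| First | Target sum | iUPD |
| First | Nontarget lesions | iSD or iPR, reset |
| First | New lesions | iSD or iPR, reset |
| Later | Target sum | iUPD |
| Later | Nontarget lesions | iSD or iPR, reset |
| Later | New lesions, burden at its smallest value | iSD or iPR, reset |
| Later | New lesions, burden at least 5 mm above its smallest value | iUPD, by the exception |

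**Illustration (assumed lesion sizes).** The target nadir is 50 mm. The threshold needs a rise of at least 20% and at least 5 mm: 50 × 1.2 = 60 mm and 50 + 5 = 55 mm, so 60 mm governs.

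1. Scan 1: target sum 50 mm and a new 15 mm lesion. The visit is iUPD.
2. Scan 2, confirmatory: target sum 50 mm, new lesion still 15 mm. Nothing has worsened and 50 is below 60, so Appendix 9 gives iSD or iPR and a reset. A rule tied to the cause would keep iUPD.
3. Scan 3: the new lesion measures 15 + 5 = 20 mm. After the reset this is a fresh iUPD that must itself be confirmed. Had scan 2 stayed iUPD, the same 5 mm rise would be iCPD.

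**Fit with the rest of Appendix 9.** The text on visits after pseudo-progression has resolved provides for earlier unequivocal nontarget progression that is still unresolved. Resolution has therefore been declared while one of its causes remains. The later-episode exception accepts in principle that new-lesion burden can block resolution, but it does not reach the first episode, nontarget lesions, or new lesions that are merely unchanged.

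**Follow-up timing.** Regular scans are 9 weeks apart up to Week 54. If the confirmatory scan falls 4 weeks after first progression, the next regular scan is 9 − 4 = 5 weeks later, inside the 4-to-8-week window for iUPD, so the two labels may lead to the same scan date. If it falls at 8 weeks, the next regular scan is 9 − 8 = 1 week later. Section 8.2.1.2 lets it be skipped because it is less than 4 weeks away, so the following one comes 18 − 8 = 10 weeks after the confirmatory scan. The gap between the labels therefore ranges from none to several weeks.

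**The case against.** The best defense is that the target-only test is a design choice. Appendix 9 anticipates lesions that remain after iSD or iPR, keeps the target nadir for the whole study, keeps a separate nadir for new lesions, and restores iUPD on a 5 mm rise, an additional lesion or significant further nontarget growth. What restarts is the level of suspicion, not the measurements. All of that is correct, but it does not explain why an unchanged lesion should be called pseudo-progression, or why its later growth should need a second confirmation. The protocol does not say that the asymmetry is intended.

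Four stronger readings are tempting, and the documents do not support them:

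- That the later-episode paragraph contradicts the first-episode rule. It is worded as an exception and concerns burden that has increased.
- That each affected participant gains at least 9 weeks of iRECIST PFS. Both Appendix 9 and Table 6 (row: "Repeat tumor imaging shows iUPD by iRECIST per investigator assessment") let the next iUPD scan coincide with the regular visit. Section 9.4.1 leaves the details of the iRECIST endpoints to the supplemental SAP. Neither label is iCPD at the confirmatory scan.
- That a rate can be given. Assuming 20 to 30 of 100 participants continue past progression, 30 to 50% of those progressions are new-lesion or nontarget only, and half are unchanged gives 20 × 0.30 × 0.5 = 3 to 30 × 0.50 × 0.5 = 7.5 per 100. None of these inputs is in the documents.
- That the primary result or the expansion decision is affected. Expansion rests on ORR, whose endpoint is defined by RECIST 1.1 or RANO.

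Whether Appendix 9 departs from the iRECIST publication it cites was not checked; that source is not among the documents.

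**Conclusion.** The point holds for the first iUPD episode, for nontarget and new-lesion causes alike: the stated rule classes unchanged, still-present progression as iSD or iPR and resets suspicion. This is a misclassification written into the rule, not missing detail.

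Its reach is narrow. It touches investigator iRECIST assessments and the exploratory iRECIST ORR, DCR, DOR and PFS in non-GBM participants on the combination. The primary and secondary endpoints do not use the rule, and no hypothesis is tested. The bias probably favors the combination, because unresolved progression can be counted as stable disease or response and its confirmation can be deferred. That direction rests on the assumption that the supplemental SAP builds the iRECIST endpoints from these visit labels. The size cannot be derived from the documents. The correction is worth making because it is cheap and specific.

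**What to change.** For the exploratory iRECIST derivation, keep the visit as iUPD when no confirming factor occurs and at least one factor that caused the iUPD is still present:

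- the target sum is above the threshold;
- unequivocal nontarget progression is unresolved; or
- new lesions have not decreased, with the amount that counts as a decrease defined in advance.

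Allow iSD or iPR, and the reset, only when none of these is still present. Amend the persistence and resolution bullets in Appendix 9 and the supplemental SAP derivation to match.

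The cost is two bullets, an aligned derivation and slightly less favorable exploratory results. The analysis needs no new scans. If the collected data do not record which factor caused each iUPD and whether it remains, report a sensitivity analysis and state the limitation.

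The iUPD row of Table 6 differs from the iSD, iPR or iCR row in rescan timing and, for clinically unstable participants, in treatment. The sponsor must reconcile those rows with the corrected definition. No treatment or stopping rule is proposed here.

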10.10 Appendix 10: Response Assessment in Neuro-Oncology (RANO) Response Criteria

Treatment response assessment will be based on the RANO criteria (Wen 2010), using a combination of clinical and imaging data. At baseline, tumor burden is documented by selection of lesions that will be followed quantitatively (target lesions) and qualitatively (nontarget). At each visit afterward, imaging assessment consists of evaluating target and nontarget lesions, searching for new lesions, and review of the abnormalities on T2/FLAIR images. These assessments are combined into a radiographic response, which is then combined with clinical performance status and steroid dose information to determine the overall response for each visit. Endpoint information, such as the best overall response, is determined from the sequence of visit responses as described in the SAP.

Scan acquisition

Imaging will be acquired using the standardized brain tumor imaging protocol (Ellingson 2015). It will include pre- and post-contrast T1-weighted MRI, as well as T2/FLAIR and diffusion-weighted imaging. The same technique should be used at baseline and all follow-up scans.

Lesion measurements

Lesions should be measured on T1 weighted postgadolinium images, in the axial plane. The 2 maximal perpendicular outer diameters of each enhancing lesion should be measured. In lesions which have cystic components, areas of necrosis, or surgical cavities, every effort should be made to measure only the solid portions of the lesion, excluding the nonsolid components. In particular, if a patient has a surgical cavity surrounded by enhancement, the cavity should not be included in the measurement. If there is nodular enhancement associated with the cavity, the nodular component alone should be measured.

Baseline tumor documentation

Reviewers will document baseline tumor on postcontrast T1-weighted and T2/FLAIR images. They first identify all lesions, determine whether they are measurable (can be measured), and from these choose target lesions (will be measured throughout the study). To be considered measurable, a lesion has to show enhancement, have 2 perpendicular diameters ≥ 10 mm, and be suitable for reproducible repeated measurements. Enhancing nonmeasurable lesions include all other enhancement that is strongly believed to represent tumor, but that does not meet the requirements above. Up to 5 lesions can be selected as target. Selected target lesions are measured, and the sum of products of diameters (SPD) calculated. Enhancing nontarget lesions are identified by location only. Because T2/FLAIR abnormalities are typically more diffuse than tumor enhancement, the T2/FLAIR images will be used for comparison when evaluating later visits, without identification of discrete lesions.

Radiographic response assessment

Target lesion response ([Table 16](#)) is determined by the change in the sum of diameters from baseline and from nadir (smallest measurement seen until the visit being evaluated):

Table 16 Target Lesion Response

Response	Definition
Complete response	All target lesions have completely disappeared.
Partial response	SPD decreased by $\geq 50\%$ from baseline value
Stable disease	SPD $< 50\%$ decreased from baseline, but $< 25\%$ increased from nadir
Progressive disease	SPD increased by $\geq 25\%$ from nadir value
Nonevaluable	The sum of diameters cannot be meaningfully evaluated (for example, because of technical factors such as scan quality that obscure one or more target lesions).

Nontarget lesion response ([Table 17](#)) is determined by visual inspection of enhancing nontarget lesions collectively and classification into a response category.

Table 17 Lesion Response for Enhancing Nontarget Lesions

Response	Definition
Complete response	All enhancing nontarget lesions have disappeared completely
Stable disease	Enhancing lesions present, showing no definite growth from the visit where they were smallest
Progressive disease	Unequivocal progression of enhancing lesions (see below)
Nonevaluable	The sum of diameters cannot be meaningfully evaluated (for example, because of technical factors such as scan quality that obscure one or more target lesions)

Note on progressive disease: The general approach is that nontarget lesions can be the basis for a determination of progressive disease if it is clear, in the context of the entire scan, that there has been a sufficient increase in the tumor burden to show that treatment has failed.

New lesions are assessed in a binary yes/no fashion. If any new enhancing lesions are present, and the reviewer is confident that these are due to the presence of new malignancy, the response is “Yes,” otherwise, it is “No.” New lesions do not need to meet the size criteria for being considered measurable at baseline, but must, in the best judgment of the reviewer, be true tumor lesions rather than benign or incidental findings, or caused by some comorbidity. If the lesion is uncertain, it should be followed. If later scans reveal it to be a true lesion, the record can be retrospectively updated to show the new lesion at the time it was first identified.

The T2/FLAIR images are reviewed to determine whether there has been an unequivocal increase in tumor-related T2/FLAIR abnormality. This is performed with reference to the scan at which the T2/FLAIR abnormality is smallest (analogous to the nadir measurement for target lesions), and classified as increase, decreased, or unchanged. Because of the frequently diffuse nature of the T2/FLAIR abnormality, it is performed at the scan level rather than by

evaluation of discrete T2/FLAIR lesions. The reviewer must be confident that any recorded increase in T2/FLAIR abnormality is due to tumor rather than some alternative etiology (such as infection, infarction, demyelination, or other causes). If there is question about whether a change seen on T2/FLAIR represents progression, the participant continues to the next scheduled scan. If the subsequent scan confirms progression, the date of progression is assigned retrospectively to the visit where the T2/FLAIR changes were first observed.

Target, nontarget, and new lesions are combined into a radiographic response (Table 18) as follows:

Table 18 Radiographic Response

Target lesions	Enhancing Nontarget lesions	FLAIR/T2 lesions	New lesions	Radiographic Response
CR	CR	No increase	No	CR
CR	SD or NE	No increase	No	PR
PR	CR, SD, or NE	No increase	No	PR
SD	CR, SD, or NE	No increase	No	SD
NED	CR, SD, or NE	No increase	No	NE
PD	Any	Any	Yes/No	PD
Any	PD	Any	Yes/No	PD
Any	Any	Any	Yes	PD
Any	Any	Increased	Yes/No	PD
NA	CR	No increase	No	CR
NA	SD	No increase	No	SD
NA	NA	No increase	No	NED

CR = complete response; FLAIR = fluid-attenuated inversion recovery; NA = no lesions of this type were present at baseline; NED = no evidence of disease (no enhancing lesions were present at baseline, and no new lesions have appeared); PD = progressive disease; PR = partial response; SD = stable disease.

Pseudoprogression associated with radiotherapy

If new or increased enhancement is seen within 12 weeks of the completion of radiation therapy, but the participant is clinically stable and the investigator believes that the changes may be due to pseudoprogression, the participant may remain on treatment. A second scan should be performed, at least 6 weeks after the initial scan. If the enhancement continues to grow on this scan, progression is considered to have been confirmed at the time of the initial scan that showed increased enhancement. If the enhancement has stabilized or decreased on this second scan, the initial scan will be considered to have been confirmed as pseudoprogression. For endpoint assessment purposes, the initial scan will be equivalent to stable disease. On subsequent scans, in cases of confirmed pseudoprogression, all scans before the scan at which pseudoprogression was seen will be excluded when choosing the nadir value against which the size of enhancing lesions is compared.

If the new or increased enhancement occurs in an area that is known to be outside the irradiated area (outside the 80% isodose line), or if the participant shows clinical deterioration not caused by a comorbid condition or changes in steroid dosing, pseudoprogression will not be considered.

Overall Response

To make a final response determination, the radiographic response (from table above) is combined with assessments of clinical status and of corticosteroid dose.

Clinical status is measured using the Karnofsky Performance Scale. A participant's status is considered "stable" if there has been no definite decline in age-adjusted performance from their baseline state, and is considered "worsening" if there has been definite decline in age-adjusted performance that is not attributable to a non-tumor-related cause. Examples of definite decline include a decline from 100 or 90 to 70 or less, a decline of at least 20 points from 80 or less, or a decline from any baseline to 50 or less, unless attributable to comorbid events or changes in corticosteroid dose.

Steroid dose is defined as the average daily dose since last visit. A dose of "none" means no corticosteroids above physiologic replacement dose. The dose is considered "stable" if it is unchanged or decreased from the visit at which the scans showed the smallest tumor burden. The dose is considered "increased" if it has increased from the visit at which the scans showed the smallest tumor burden.

For any overall response except PD, all the components of the definition (radiological, neurological, and steroid dose) must be present ([Table 19](#)). However, either radiological progression or clinical deterioration (not attributable to a nontumor-related cause) qualifies a participant for PD. However, an increase in steroid dose alone is not sufficient for an overall visit response of PD in the absence of clinical or radiological evidence of progression. A participant with a radiological response of stable disease, and without neurological evidence of progression, but requiring an increased dose of steroids, would still be considered stable disease overall at that visit (because increase in steroids alone is not PD). However, the participant will be reassessed at the next visit. If either radiological or neurological progression is documented at that next visit, the visit at which the increased dose was first observed would be retroactively reassessed as PD overall.

Table 19 Overall Response

Radiographic Response	Clinical Performance	Steroid Dose	Overall Response
CR	Stable	None	CR
CR	Stable	Stable or increased	PR
PR	Stable	Stable	PR
PR	Stable	Increased	SD
SD	Stable	Stable	SD
SD	Stable	Increased	SD or PD ^a
PD	Any	Any	PD
Any	Worsening	Any	PD
NE	Stable	Increased	NE or PD ^a
NED	Stable	Increased	NED or PD ^a

CR = complete response; NA = no lesions of this type were present at baseline; NED = no evidence of disease (no enhancing lesions were present at baseline, and no new lesions have appeared); PD = progressive disease; PR = partial response; SD = stable disease.

^a PD should not be based on an increase in steroid dose alone, unless confirmed by radiographic or clinical deterioration. If the steroid dose is increased while the radiographic assessment and clinical performance are stable, the participant should be re-evaluated at the next visit. If clinical or radiographic deterioration has occurred, progression can be retrospectively assigned at the visit when the steroid dose was increased.

Pseudoresponse and response confirmation

Pseudoresponse is a phenomenon observed in patients treated with antiangiogenic therapy, and manifests as a transient decrease in tumor enhancement that does not reflect a true reduction in tumor burden. To avoid mistaken reporting of pseudoresponse as OR, a visit response of PR or CR must be confirmed with a scan performed at least 4 weeks later that shows the same category of response or better. That is, a PR can be confirmed with a subsequent PR or CR, and a CR must be confirmed with a subsequent CR.

